CCMO	Central Committee on Research Involving Human Subjects; in Dutch: Centrale Commissie Mensgebonden Onderzoek
DLCO	Diffusing capacity of the Lungs for Carbon Monoxide
DSMB	Data Safety Monitoring Board
ECM	Extracellular Matrix
EU	European Union
EudraCT	European drug regulatory affairs Clinical Trials
FAP	Fibroblast Activation Protein
FAPI	Fibroblast Activation Protein Inhibitors
GCP	Good Clinical Practice
GMP	Good Manufacturing Practice
GDPR	General Data Protection Regulation; in Dutch: Algemene Verordening Gegevensbescherming (AVG)
HRCT	High-Resolution Computed Tomography
IB	Investigator's Brochure
IC	Informed Consent
ILA	Interstitial Lung Abnormalities
IMP	Investigational Medicinal Product
IMPD	Investigational Medicinal Product Dossier
METC	Medical research ethics committee (MREC); in Dutch: medisch-ethische toetsingscommissie (METC)
MBq	Megabecquerels
PASC	Post-Acute Sequelae of SARS-CoV-2 Infection
PET/CT	Positron emission tomography/computerized tomography
(S)AE	(Serious) Adverse Event
SPC	Summary of Product Characteristics; in Dutch: officiële productinformatie IB1-tekst

Sponsor	The sponsor is the party that commissions the organisation or performance of the research, for example a pharmaceutical company, academic hospital, scientific organisation or investigator. A party that provides funding for a study but does not commission it is not regarded as the sponsor, but referred to as a subsidising party.
SUSAR	Suspected Unexpected Serious Adverse Reaction
SUV	Standardized Uptake Value
TLF	Total Lesion Fibrosis
UAVG	Dutch Act on Implementation of the General Data Protection Regulation; in Dutch: Uitvoeringswet AVG
VC	Vital Capacity
WMO	Medical Research Involving Human Subjects Act; in Dutch: Wet Medisch-wetenschappelijk Onderzoek met Mensen
wIFAPI-MAV	Whole Lung FAPI-Metabolic Active Volume
wITL-FAPI	Whole Lung Total Lesion-FAPI
wISUV	Whole Lung Standardised Uptake Value

SUMMARY

Rationale: The pathogenesis of post-acute COVID-19 with respiratory complaints remains unknown. We aim to explore the pulmonary pattern and fibrosis activity in patients with post-acute COVID-19 with respiratory complaints using ^{68}Ga -FAPI Positron Emission Tomography-Computed Tomography (PET/CT) imaging.

Objective: To relate pulmonary fibroblast activity, measured by FAPI-PET/CT at least 3 months after hospital discharge, to interstitial lung abnormalities on HRCT at the same time point in post-acute COVID-19 patients with respiratory complaints.

Study design: This is a ZonMw funded single center prospective observational cohort study of post-acute COVID-19 patients with respiratory complaints.

Study population: We will recruit 20 adult patients with post-acute COVID-19 and respiratory complaints that will undergo ^{68}Ga -FAPI PET/CT imaging to establish pulmonary fibrosis activity.

Main study parameters/endpoints: To assess the degree of Fibroblast Activation Protein expression on ^{68}Ga -FAPI PET/CT at least 3 months after hospital discharge and to relate this to interstitial lung abnormalities on HRCT at the same time point.

1. INTRODUCTION AND RATIONALE

1.1 Background to pulmonary fibrosis in post-COVID-19 syndrome

The ongoing pandemic caused by the novel coronavirus (SARS-COV-2), which causes the disease known as COVID-19, is leading to another epidemic of post-acute patients with persistent health impairments. The majority of COVID-19 patients survive the infection and acute illness, however, the long-term health effects are largely unknown. A substantial proportion of patients experience long-term symptoms, ranging from pure respiratory symptoms to disabling fatigue and mental issues (1,2), referred to as long COVID-19 or post-acute sequelae of COVID-19 (PASC). It has been shown that the majority of COVID-19 survivors have some persistent interstitial lung abnormalities (ILA) on HRCT, most extensive in post-intensive care unit patients and patients with longer duration of hospitalization (3,4). However, both the evolution of these ILA and their nature are unknown, since they can reflect ongoing inflammation, residual areas of organizing pneumonia, or early fibrosis. This may result in persistent pulmonary complaints, with or without an abnormal lung function test, with up to 76% of the patients still having normal diffuse capacity (5). Although chest computed tomography (CT) has been shown to be a useful tool in identifying lung abnormalities in patients with PASC, it does not provide information about the pathogenesis and possible targets for intervention. Advanced molecular imaging to assess ongoing fibroblast activity has the potential to provide a pathophysiological model and, possibly, personalized targeted pharmacological interventions. The recently developed ^{68}Ga -FAPI PET tracer has this potential.

Fibroblast activation protein (FAP) alpha is a type II transmembrane protease with dipeptidyl peptidase and endopeptidase activity which is induced in fibroblasts upon activation and is negligible or absent in resting fibroblasts or other cell types (6). The recently developed radiolabeled quinoline-based positron emission tomography (PET) tracers binding to FAP, like ^{68}Ga -FAPI, demonstrate tracer uptake in various tumor entities (7). Expression of FAP as detected by ^{68}Ga -FAPI PET also correlates with fibrotic activity and disease progression in the lungs of patients with systemic sclerosis-associated interstitial lung disease (8).

^{68}Ga -FAPI PET can therefore aid in the understanding of the pathophysiology of PASC with persistent pulmonary complaints. With ^{68}Ga -FAPI PET we aim to quantify the fibroblastic activity in relation to the percentage of interstitial lung abnormalities on high resolution computed tomography (HRCT), lung function testing including diffusing capacity of the lungs for carbon monoxide (DLCO) and vital capacity (VC), fibrotic and inflammatory blood markers, systemic and upper respiratory tract cellular phenotypes as determined by single cell RNA sequencing, 6-minute walking test (6-MWT) and self-reported daily impairments measured by EQ-5D questionnaire of patients with PASC at >3 months after hospital

discharge and, in case of persisting symptoms, at 8-10 months after ^{68}Ga -FAPI PET/CT scan.

1.2 Study Aim

With ^{68}Ga -FAPI PET we aim to quantify the fibroblastic activity in relation to the interstitial lung abnormalities on high resolution computed tomography (HRCT), lung function including DLCO and VC, fibrotic and inflammatory blood markers, systemic and upper respiratory tract cellular phenotypes determined by single cell RNA sequencing, 6-MWT and self-reported daily impairments measured by EQ-5D questionnaire in post-acute COVID-19 patients.

1.3 Research Hypothesis

We hypothesize that increased fibroblast activity can be found on PET and interstitial lung abnormalities on HRCT in post-acute COVID19 patients with pulmonary complaints, with a match and/or mismatching pattern between both imaging modalities.

1.4 Rationale for Study

The quantification of pulmonary fibrosis activity using ^{68}Ga -FAPI PET has the ability to advance our understanding of the pathological processes that occur in post-acute COVID-19 patients with persistent pulmonary complaints. It is unknown whether the persistent respiratory impairments and fibrotic lesions on HRCT are the result of ongoing fibroblast activity. The findings from this study will provide us with much needed pathophysiological insight in post-acute COVID-19 and result in identification of patients that may benefit in the future from anti-fibrotic medication to enhance pulmonary recovery.

2. OBJECTIVES

Primary objectives

To relate pulmonary fibroblast activity, measured by FAPI-PET/CT at least 3 months after hospital discharge, to interstitial lung abnormalities on HRCT at the same time point (T_0) in post-acute COVID-19 patients with respiratory complaints.

Secondary objectives

To relate pulmonary fibroblast activity, measured by FAPI-PET/CT, to specific fibrosis and inflammatory blood markers, upper respiratory and systemic cell phenotypes, 6-MWT, lung function including DLCO and VC, and self-reported daily impairments measured by the EQ-5D questionnaire at the same time point (T_1) and to HRCT findings, EQ-5D and 6-MWT, in case of persistent respiratory complaints 8-10 months after timepoint T_0 .

3. STUDY DESIGN

This is a prospective observational cohort study.

[figure not shown]

Figure 1. Flow chart of study procedures.

4. STUDY POPULATION

4.1 Population (base)

We will recruit 20 hospital-discharged adult patients with post-acute COVID-19 and respiratory complaints.

4.3 Exclusion criteria

Subjects should not enter the study if any of the following criteria are fulfilled:

- Inability or unwilling to give informed consent.
- History of claustrophobia or feeling of inability to tolerate supine position for the PET/CT scans.
- Severe or significant comorbidity, defined as COPD GOLD stage II or higher, known interstitial lung disease and/or an ASA score (11) of IV and higher.
- Women who are pregnant or breastfeeding.

4.4 Sample size calculation

This is an explorative study and a power analysis cannot be applied to calculate the number of included patients. The total number will be 20 patients, as performed usually in these kinds of feasibility studies (12).

5. TREATMENT OF SUBJECTS

Not applicable.

6. INVESTIGATIONAL PRODUCT

6.1 Name and description of investigational product(s)

⁶⁸Ga–fibroblast activation protein inhibitor ([⁶⁸Ga]FAPI-46) is a quinoline-based radiopharmaceutical used for the in vivo detection of the fibroblast activation protein using positron emission tomography (PET). Chemical name is Gallium;(R)-2,2',2''-(10-(2-(4-(3-((4-(2-(2-cyano-4,4-difluoropyrrolidin-1-yl)-2-oxoethyl)carbamoyl)quinolin-6-yl)(methyl)amino)propyl)piperazin-1-yl)-2-oxoethyl)1,4,7,10,tetraazacyclododecane-1,4,7-triyl)triacetate. [⁶⁸Ga]FAPI-46 is produced as a sterile, intravenously injectable solution of the radiopharmaceutical, containing 10% ethanol in 0.9% phosphate buffered sodium chloride (PBS) solution (v/v)

6.2 Summary of findings from non-clinical studies

Please see the Investigational Medicinal Product Dossier (IMPD).

6.3 Summary of findings from clinical studies

See section 13.1.

6.4 Summary of known and potential risks and benefits

See Section 13.1.

6.5 Description and justification of route of administration and dosage

⁶⁸Ga-FAPI has been administered to humans and demonstrated its ability to detect areas of fibrosis activity within different cancers at acceptable radiation doses (1.6 mSv) (13). No other available route of administration.

6.6 Dosages, dosage modifications and method of administration

Intravenous injection of 200 megabecquerels (MBq) ⁶⁸Ga-FAPI.

6.7 Preparation and labelling of Investigational Medicinal Product

⁶⁸Ga-FAPI will be manufactured locally in a GMP licensed facility adjacent to the PET scanners. Quality Control will be performed on a sample of the final product before releasing ⁶⁸Ga-FAPI for use against pre-established specifications including radiochemical and chemical purity, residual solvents, endotoxin content and pH. Sterility will also be confirmed post release.

6.8 Drug accountability

Not applicable.

7. NON-INVESTIGATIONAL PRODUCT

Not applicable.

8. METHODS

8.1 Study endpoints

8.1.1 Main study endpoint

To assess the degree of Fibroblast Activation Protein expression on ^{68}Ga -FAPI PET/CT at least 3 months after hospital discharge (timepoint T_0) and to relate this to interstitial lung abnormalities on HRCT at the same time point.

8.1.2 Secondary study endpoints

1. To relate the degree of Fibroblast Activation Protein expression at least 3 months after hospital discharge to DLCO and VC, ECM and inflammatory blood markers, systemic and upper respiratory tract cellular phenotypes, 6MWT and EQ-5D at the same time point.
2. To relate the degree of Fibroblast Activation Protein expression at least 3 months after hospital discharge to interstitial lung abnormalities on HRCT, 6MWT and EQ5D 8-10 months after timepoint T_0 in patients with persisting respiratory complaints.

8.2 Randomisation, blinding and treatment allocation

Not applicable.

8.3 Study procedures

8.3.1 PET Radiotracer ^{68}Ga -FAPI production

^{68}Ga -FAPI will be manufactured locally in a GMP licensed facility adjacent to the PET scanners. Quality Control will be performed on a sample of the final product before releasing ^{68}Ga -FAPI for use against pre-established specifications including radiochemical and chemical purity, residual solvents, endotoxin content and pH. Sterility will also be confirmed post release.

8.3.2 PET/CT imaging

To assess pulmonary fibrosis activity, we will perform ^{68}Ga -FAPI biodistribution studies in 20 post-COVID-19 patients using established protocols. After insertion of a peripheral intravenous catheter, each subject will undergo a PET and low dose CT (PET/CT) scan (Vision or QUADRA Biograph mCT, Siemens Medical Systems, Erlangen, Germany), from head to proximal lower limb 60 minutes following intravenous injection of 200 MBq ^{68}Ga -

FAPI. An HRCT scan will be performed immediately afterwards, on the same scanner. Total scanning time will be 15 minutes.

If HRCT, as ordered by attending pulmonologist as part of regular care, is repeated 11-13 months after hospital discharge for persisting pulmonary complaints, this data will be used for analysis.

PET analysis:

⁶⁸Ga-FAPI uptake as a measure of fibrosis activity in the lung will be evaluated by visual assessment of the active pulmonary ⁶⁸Ga-FAPI lesions. Increased ⁶⁸Ga-FAPI uptake will be compared with the muscle background uptake and defined as being positive when higher, and verified by follow-up with HRCT. For quantitative analysis, a specialized software platform from Hermes Hybrid 3D (Hermes Medical Solutions AB, Stockholm, Sweden) will be used. The mean and maximum standardized uptake value (SUV) and the metabolic active volume (MAV) normalized to body weight will be manually computed for the active pulmonary lesions and healthy tissues by drawing a 3-dimensional volume of interest. Multiplication of SUV_{mean} and MAV results in total lesion FAPI (TL-FAPI). Whole-lung FAPI-MAV (wIFAPI-MAV) can then be calculated by summation of MAV over all lung areas. Whole lung mean SUV (wSUV_{mean}) will be calculated as the mean of the SUV values of all five pulmonary lobes. These parameters will allow us to calculate whole lung TL-FAPI (wTL-FAPI) by multiplying wIFAPI-MAV with SUV_{mean}.

SUV_{max} ratio for the pulmonary hotspot will be defined as the quotient of the SUV_{max} of this lesion and the normal muscular tissue, and target-to-background ratio (TBR) for active pulmonary lesions will be calculated according to the formula: $TBR = tSUV_{max}/mSUV_{mean}$, where tSUV_{max} is the maximum SUV of lung lesion, and mSUV_{mean} is the mean SUV of muscle.

HRCT analysis:

In the absence of a validated scoring system to evaluate HRCT scans for the presence of fibrosis in PASC, we will use a validated scoring system developed by Desai and Goh for evaluation of interstitial lung abnormalities on HRCT in patients with systemic sclerosis associated interstitial lung disease, idiopathic pulmonary fibrosis and idiopathic non-specific interstitial pneumonia (14,15). HRCT scans will be reviewed at five levels. At each level, four features of fibrosis will be quantified: the extent of interstitial lung disease, the relative proportions of interstitial lung disease made up of a reticular pattern and ground-glass opacification, the amount of emphysema, and the coarseness of fibrosis. Finally, an overall grade of interstitial lung disease depending on the relative extent of a reticular pattern will be given.

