13. STRUCTURED RISK ANALYSIS

13.1 Potential issues of concern

There are some potential hazards of the investigations that we will perform as part of the trial. The main issues relate to exposure to ionising radiation and arterial line insertion.

a. Level of knowledge about mechanism of action

Ionising radiation can cause cancer which manifests itself after many years or decades. The estimated associated risk of developing fatal cancer is proportional to dose and also to the participant's age at the time of exposure. The risk for younger people is higher than for older people and the risk for females is higher than for males of the same age. According to report 26 of the Netherlands Commission on Radiation Dosimetry, radiation exposure for this study must be in category IIb at most. Since total radiation exposure in this study is 5 mSv, males must be at least 10 years old and females must be at least 20 years old to fall into category IIb (18).

A recent study scanned 25 patients following injection of between 198 and 299 MBq ⁶⁸Ga-FAPI-4 (19). With consideration to minimising dose, all participants in this study will receive a maximum of 200 MBq per IV administration of ⁶⁸Ga-FAPI-4 with a total dose of 1.6 mSv. All participants will receive an additional dose from the (low dose) CT-component of the scanner (an additional 0.7 mSv), including a baseline HRCT (2.7 mSv) so in total each PET/CT including HRCT will be associated with 5mSv of radiation exposure (see Supplement Radiation dose calculation). The follow-up chest HRCTs will be clinically performed.

b. Previous exposure of human beings with the test product(s) and/or products with a similar biological mechanism

[⁶⁸Ga]FAPI-46 has been applied in several human studies in patients with various types of cancer (12,13,19–21) and pulmonary fibrosis (8). No adverse events have been reported in these studies.

c. Can the primary or secondary mechanism be induced in animals and/or in *ex-vivo* human cell material?

Not for this study as we are looking into pulmonary fibrosis timeline in humans.

d. Selectivity of the mechanism to target tissue in animals and/or human beings

Not applicable.

e. Analysis of potential effect

Please see: Synthesis.

f. Pharmacokinetic considerations

Not applicable.

g. Study population

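### The FAPI positivity rule invokes an unnamed HRCT check without saying whether it decides which lesions enter the PET totals that are then correlated with HRCT

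*Combined protocol and SAP*

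**What the plan says.** Under PET analysis, Section 8.3.2 gives one rule for positive uptake. Lung uptake "will be compared with the muscle background uptake and defined as being positive when higher, and verified by follow-up with HRCT". SUV and volume measures "will be manually computed for the active pulmonary lesions and healthy tissues by drawing a 3-dimensional volume of interest". The whole-lung volume "can then be calculated by summation of MAV over all lung areas", and whole-lung mean SUV is averaged over the five lobes. Section 10.1 expresses FAP expression through the whole-lung volume and whole-lung TL-FAPI and correlates the FAPI-PET/CT findings with HRCT, with significance at p < 0.05.

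Two HRCT scans could be the verifier. Every patient has one directly after the PET/CT, at T0. Some have another in regular care: if HRCT "is repeated 11-13 months after hospital discharge for persisting pulmonary complaints, this data will be used for analysis". Section 13.1 calls the T0 scan the baseline one and adds: "The follow-up chest HRCTs will be clinically performed".

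Each candidate is also a comparator. Section 8.1.1 relates FAP expression to the T0 HRCT. Section 8.1.2, item 2, relates it to HRCT 8-10 months after T0 in patients whose complaints persist. On reading, Section 8.3.2 says "HRCT scans will be reviewed at five levels" and lists the features scored. It gives no reader, masking or reading order for either modality.

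**The concern.** The verification clause can be read in two ways. It may be a later plausibility check that leaves the PET measure alone, or a condition that a lesion must meet to be counted. The plan gives no rule for a lesion above muscle that has no HRCT correlate, or for one in a patient who is never rescanned.

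Under the second reading, one side of the correlation is partly built from the other. Section 1.3 expects a matching and/or mismatching pattern between the modalities; lesions seen on PET but not on HRCT are one half of the mismatch, and they would be removed by definition. A reader of the results could not tell whether such lesions were absent or discarded, or how much of a reported correlation came from the counting rule. Hand-drawn volumes with no stated reading order leave room for the same influence even without a formal rule.

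**Working it through.** **Which scan.** The word follow-up, together with Section 13.1, favours the later regular-care scan. The two timings given for it agree if T0 falls three months after discharge (3 + 8 = 11 and 3 + 10 = 13 months), so I treat it as the HRCT of secondary endpoint 2. It exists only for patients rescanned for persisting complaints.

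**Size if HRCT decided which lesions count.** The plan states no figure to reproduce. From the documents: 20 patients, Pearson or Spearman, p < 0.05. All else is assumed:
- two-sided test, five lung regions per patient, PET and HRCT truly unrelated, prevalence 0.5 for each
- lesion volume and HRCT extent equal across regions, or lognormal with log-SD 0.5 or 1
- a share d of unverified lesions dropped
- 10,000 simulated trials per setting.

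The critical value is r = t/√(n − 2 + t²). For n = 20, t = 2.101, so r = 2.101/√(18 + 4.414) = 0.444.

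*Same scan gates and is correlated.* With equal volumes, the chance that a region holds a counted lesion is m = 0.5(1 − d/2). Its covariance with the HRCT indicator is 0.25 − 0.5m = d/8, and r = (d/8)/√[m(1 − m) × 0.25].
- d = 0: r = 0.
- d = 0.5: m = 0.375, r = 0.0625/√(0.2344 × 0.25) = 0.26.
- d = 1: m = 0.25, r = 0.125/√(0.1875 × 0.25) = 0.58.

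The simulation agrees (0.25 and 0.57 at n = 20). Ranges below span Pearson, Spearman and the three volume settings.

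| Gate and analysis | Unverified lesions dropped | Mean r | p < 0.05 |
|---|---|---|---|
| None, n = 20 | none | 0.00 | about 5% |
| T0 scan, primary, n = 20 | a quarter | not tabulated | 5% to 9% |
| T0 scan, primary, n = 20 | half | 0.08 to 0.25 | 7% to 19% |
| T0 scan, primary, n = 20 | all | 0.19 to 0.57 | 15% to 79% |
| Later scan, endpoint 2, 10 rescanned | half | not tabulated | about 7% to 11% |
| Later scan, endpoint 2, 10 rescanned | all | 0.21 to 0.55 | 12% to 44% |

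With all dropped, prevalences of 0.3 to 0.7 (log-SD 0.5 or 1) widen the T0 row to 0.10 to 0.61 and 8% to 84%. With 5 to 15 patients rescanned, endpoint 2 gives 9% to 66%. A different model for the T0 gate (Poisson lesion counts with mean 6, log-SD 0.7, HRCT extent averaging 0.15 to 0.50, Spearman) gives 81% to 95% if all lesions depend on HRCT, 13% to 21% if half do, and 4% to 5% if none do.

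*Later scan gates, T0 HRCT is correlated (primary).* Half of 20 patients are rescanned, and 50% to 100% of T0 abnormalities persist.
- Rescanning at random, lesions in unscanned patients kept: mean r 0.04 to 0.24.
- Same, but the chance of a rescan correlated with T0 extent: at 0.3, −0.07 to 0.11; at 0.5, −0.18 to 0.02; at 0.7, −0.31 to −0.06.
- Lesions in unscanned patients not counted, rescanning at random: 0.09 to 0.28, and higher if rescanning is selective.

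The sign can turn because the gate strips lesions only from rescanned patients. If they have the more extensive T0 disease, their PET totals fall while those of patients with little disease stay whole. This gate also removes lesions that matched HRCT at T0 and later resolved. With a real ungated association of 0.38 (random rescanning, log-SD 0.5, persistence 0.5), the correlation fell to 0.31.

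**The case against.** The strongest case is that nothing in the plan excludes an unverified lesion. Uptake above muscle is a complete PET-only definition. Verification appears with the visual assessment, and the quantitative procedure that follows never mentions it. Volumes are summed over all lung areas, mean SUV covers all five lobes, healthy tissue is outlined too, and Section 1.3 anticipates mismatch. This stands: a reader might infer that the PET measure is circular by design, and the text does not support that. It does not close the question, because the summed volumes come from lesions drawn by hand as active, and the only positivity rule carries the HRCT clause.

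A reader might also infer that any HRCT gate would inflate the primary correlation. The calculations do not support that for the later scan, which is the better-supported reading.

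Nor does the Not applicable entry under "8.2 Randomisation, blinding and treatment allocation" show that readers see each other's results. That heading concerns treatment allocation; the point is only that no section describes separate reading.

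Finally, the sizes rest wholly on assumed inputs, reduce HRCT to present or absent by region, and model volume without an SUV term. Section 10 calls all outcomes exploratory. Both points stand and limit the issue to interpretability.

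**Conclusion.** The clause is ambiguous in a place that matters: it touches both the primary correlation and secondary endpoint 2, and the plan offers no separate reading as protection. Circularity is a risk that the text leaves open, and the balance of wording favours totals that do not depend on HRCT.

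If HRCT did decide which lesions count, two consequences follow. PET-positive/HRCT-negative mismatch would be removed by rule. Under the assumptions above, the correlation would be biased upward wherever one scan both gates and is correlated: T0 on the primary, or the later scan on secondary endpoint 2. The amount runs from negligible when a quarter of unverified lesions are dropped to large when all are. For a later-scan gate on the primary, the direction depends on who is rescanned and on how lesions in unscanned patients are handled. This is a cheap improvement, held with medium confidence.

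**What to change.** Replace the verification clause in Section 8.3.2 with text such as:

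> A lesion is FAPI-positive when its uptake on PET is higher than muscle. Positivity and the volumes entering wlFAPI-MAV and wlTL-FAPI are fixed from the PET/CT before the HRCT result is consulted, and HRCT is scored without sight of the PET result. Agreement with HRCT is reported separately, naming the scan used (T0 or later regular-care), and never changes the PET totals.

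If verification was only ever meant as a later check, the last sentence alone settles the ambiguity; the middle sentence adds the protection of separate reading.

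The cost is a short protocol text and a fixed reading order, with no extra scans. The documents do not say whether the low-dose CT shows lobe borders well enough; if it does not, HRCT can be used for borders only and not for positivity. The downside is that some false-positive PET lesions stay in the totals and appear as mismatches.

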10.1 Primary study parameter(s)

Descriptive statistics will be used to analyze the degree of Fibroblast Activation Protein expression on ^{68}Ga -FAPI PET/CT, expressed as wTL-FAPI and wFAPI-MAV. Correlations between FAPI-PET/CT findings and HRCT findings will be assessed using Pearson's correlation coefficient or Spearman's rank-order correlation. A p-value of <0.05 will be considered significant.

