10.2 Secondary study parameter(s)

The correlation between FAPI PET/CT findings and lung function (DLCO and VC), 6-MWT, EQ5D and HRCT fibrosis findings will be assessed using Pearson's correlation coefficient or Spearman's rank-order correlation. Statistical significance between consecutive tests will be assessed using analysis of variance, paired t-test or Wilcoxon signed-rank test, as appropriate. A p-value of <0.05 will be considered significant.

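### Emphysema is scored under the heading of fibrosis and is not kept out of the HRCT findings correlated with FAPI, and the FAPI-DLCO correlation makes no use of the score

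*Combined protocol and SAP*

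**What the plan says.** Section 8.3.2 (HRCT analysis) adopts a published scoring system "for evaluation of interstitial lung abnormalities on HRCT in patients with systemic sclerosis associated interstitial lung disease" and two other fibrotic lung diseases. Scans are read at five levels. "At each level, four features of fibrosis will be quantified": the extent of interstitial lung disease (ILD), its reticular and ground-glass proportions, and then "the amount of emphysema, and the coarseness of fibrosis". Lastly, "an overall grade of interstitial lung disease depending on the relative extent of a reticular pattern will be given".

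The primary objective (section 2) and main endpoint (8.1.1) concern interstitial lung abnormalities on HRCT. Section 10.1 puts it more openly: "Correlations between FAPI-PET/CT findings and HRCT findings will be assessed using Pearson's correlation coefficient or Spearman's rank-order correlation". Section 10.2 says "The correlation between FAPI PET/CT findings and lung function (DLCO and VC), 6-MWT, EQ5D and HRCT fibrosis findings will be assessed", by Pearson or Spearman. Neither section names the HRCT items that enter. Neither gives the emphysema score any role as covariate, stratifier or sensitivity analysis.

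The only limit on emphysema at entry is in section 4.3, where severe comorbidity is "defined as COPD GOLD stage II or higher", known ILD, or ASA IV and above. Sections 4.4 and 10 set the sample at 20 patients without a power calculation and call the outcomes exploratory. Sections 10.1 and 10.2 nevertheless declare significance at p<0.05.

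**The concern.** There are two linked problems.

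**Label.** Emphysema is loss of lung tissue. It is neither fibrosis nor an interstitial abnormality. Because 8.3.2 files it under fibrosis and section 10 leaves its HRCT terms open, an analyst who follows the text could include an emphysema correlation among the results for the primary objective or the HRCT fibrosis results in 10.2.

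**Unused score.** Section 1.4 asks whether persisting respiratory impairment results from ongoing fibroblast activity. DLCO is one of the impairment measures related to FAPI in secondary endpoint 1. Emphysema is a competing cause of low DLCO, and the plan already measures it in every patient. Patients with COPD GOLD I, or with emphysema but no COPD grade, remain eligible. A raw FAPI-DLCO correlation cannot separate the two causes. It may be too weak or too strong, depending on how emphysema and FAPI uptake happen to be related in these 20 patients.

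**Working it through.** **Where emphysema stands in the text**

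| Place | HRCT term | Emphysema |
|---|---|---|
| 2 and 8.1.1 | Interstitial lung abnormalities | Outside, by meaning |
| 8.3.2, item list | Features of fibrosis | Named as one of four |
| 8.3.2, overall grade | Grade based on reticular extent | Not part of it |
| 10.1 | HRCT findings | Not excluded |
| 10.2 | HRCT fibrosis findings | Inside, if the 8.3.2 label is followed |

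The overall grade would keep emphysema out, but section 10 does not name it as the analysis variable.

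**Effect on the FAPI-DLCO correlation**

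The plan states no effect size or power, so there is no figure of its own to reproduce. What follows is an illustration.

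- From the documents: n = 20 (4.4) and significance level 0.05 (10.2). Two-sided testing is assumed, because the plan does not say.
- Assumed: the true FAPI-DLCO correlation given emphysema is p = -0.6. Emphysema explains v = 10% to 30% of DLCO variance, so r_DE = -√v = -0.316 to -0.548. The FAPI-emphysema correlation r_FE is -0.4, -0.2, 0 or +0.4.

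Raw correlation: r = p·√[(1 − r_FE²)(1 − v)] + r_FE·r_DE.

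Power by the Fisher z approximation: Φ(|atanh r|·√(n−3−k) − 1.96), where k is the number of covariates. The opposite tail is negligible.

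| r_FE | v | First term | Second term | Raw r | Power |
|---|---|---|---|---|---|
| 0 | 10% | -0.569 | 0 | -0.57 | 76% |
| 0 | 30% | -0.502 | 0 | -0.50 | 62% |
| -0.2 | 10% | -0.558 | +0.063 | -0.49 | 61% |
| -0.2 | 30% | -0.492 | +0.110 | -0.38 | 38% |
| -0.4 | 10% | -0.522 | +0.126 | -0.40 | 41% |
| -0.4 | 30% | -0.460 | +0.219 | -0.24 | 17% |
| +0.4 | 10% | -0.522 | -0.126 | -0.65 | inflated |
| +0.4 | 30% | -0.460 | -0.219 | -0.68 | inflated |

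Adjusted for emphysema (k = 1): atanh(0.6) = 0.693, and 0.693 × √16 = 2.77, which gives 79% power in every row.

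**Cost of adjusting if emphysema is irrelevant.** With v = 0 and r_FE = 0, the unadjusted power is 81.5% (0.693 × √17 = 2.86) against 79.2% adjusted, a loss of about 2 points. The critical |r| moves from 0.444 to 0.456.

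**No true FAPI-DLCO relation.** With p = 0 the raw r is r_FE·r_DE. Absolute correlations of 0.3 to 0.5 on each side give a spurious |r| of 0.09 to 0.25. The rejection rate is then about 7% to 18% instead of 5%.

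**The case against.** The strongest reply is that the label is only a loose heading. The objective and the main endpoint fix the HRCT side as interstitial lung abnormalities, the score is introduced for that purpose, and its overall grade rests on the reticular pattern. Emphysema may simply be a recorded item of the adopted system. This has force. A reader might infer that the plan tests emphysema as part of its primary analysis, but no section lists such a test. What stands is narrower: emphysema is labelled as fibrosis, and nothing in section 10 excludes it.

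A second tempting inference is that emphysema must hide the FAPI-DLCO relation, because SUV is measured per unit volume and so falls along with DLCO. The documents do not support that direction. Section 10.1 names wTL-FAPI and wFAPI-MAV. The second is a summed volume, so the dilution argument does not apply to it directly, and it reaches wTL-FAPI only through its SUVmean factor. With r_FE = +0.4 the same formula inflates the correlation. The 17% power figure needs two extreme assumptions at once. Nor does section 1.3 state a directional FAPI-DLCO hypothesis.

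Third, emphysema may be rare. Section 4.3 excludes COPD GOLD II or higher, and section 4.2 selects on severe COVID-19. If most scores are zero, a partial rank correlation will be dominated by ties and will say little. The 79% is also a Pearson-type approximation, not a calculation for ranks. Both points hold.

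Finally, the study is exploratory and the DLCO correlation is one of many. The consequence is therefore for interpretation, not for a confirmatory error rate.

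**Conclusion.** The point holds in limited form. The text mislabels emphysema and leaves it inside terms meant for interstitial abnormalities. The FAPI-DLCO correlation also ignores a competing cause that is scored in every patient.

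The size of the second problem is unknown. Under the stated assumptions the raw correlation could lie anywhere from -0.24 to -0.68 around a true partial value of -0.6. If FAPI and emphysema are unrelated, the loss is modest: power of 76% to 62%, against 79% with adjustment. If few patients have emphysema, it is small. That emphysema lowers DLCO is general physiology and is not taken from the documents. The change is worth making because it is cheap and because a partial correlation deals with either direction of bias. It does not call the study's design into question.

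**What to change.** 1. **Section 8.3.2:** list three ILD or fibrosis features (ILD extent, reticular and ground-glass proportions, coarseness), and score emphysema extent as a separate item.
2. **Sections 10.1 and 10.2:** state that the HRCT findings correlated with FAPI are the ILD features and the overall grade, not emphysema. This still leaves several candidate HRCT variables. Naming one for the primary correlation would close that related gap.
3. **Section 10.2:** beside the raw FAPI-DLCO correlation, report a partial (rank) correlation adjusted for T0 emphysema extent, labelled as an exploratory sensitivity analysis. Report how many patients have a non-zero emphysema score, so that readers can judge how informative it is.

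The cost is a few sentences and one extra correlation from data already collected. The adjustment uses one degree of freedom, about 2 points of power at r = -0.6 if emphysema plays no part. It adds little if most emphysema scores are zero.
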